5.3. Methods to Manage Missing Data

For the MMRM analysis, all available windowed data through Week 52 will be included in the analysis with no explicit imputation of missing data. For participants with the endpoint observed at the primary timepoint, values of the endpoint at other timepoints do not influence the estimate at the primary endpoint and will reduce the variability. For participants with the endpoint missing at the primary timepoint, values at other timepoints influence the estimate at the primary timepoint implicitly. The MMRM analysis is unbiased under the assumption that all missing data are missing at random (MAR) and is valid under the assumption that participants who discontinue would behave similarly to other participants in the same treatment group had they not discontinued. Under Primary Estimand, this assumption is scientifically plausible since fordadistrogene movaparovec is intended to be used as a gene replacement therapy (ie, disease-modifying). Participants receive a single infusion of investigational product (fordadistrogene movaparovec or placebo) on Day 1 and thus, discontinuation from treatment is not possible, and it is reasonable to assume that participants who discontinue from the study would behave similarly to other participants in the same treatment group had they not discontinued from the study.

To assess the sensitivity of the MMRM analysis under Primary Estimand to model assumptions and to verify the robustness of the estimates to departures from the assumptions, a copy increments in reference imputation approach will be used [Cro et al, 2016]³. Missing data in the reference (placebo) group will be imputed under the MAR assumption, while missing data in the fordadistrogene movaparvovec group will be imputed under a missing not at random (MNAR) assumption where the missing data starts from the last non-missing value and then changes to following the differences in the placebo group profile. This assumes that the participant profile in the fordadistrogene movaparvovec groups tracks that of the placebo group, but starting from the benefit already obtained, which reflects the fordadistrogene movaparvovec having a benefit but participants who drop out are then experiencing a disease progression as a worst case scenario.

A tipping point analysis will also be performed to assess the sensitivity of the MMRM analysis under Primary Estimand and assess the impact of missing data.

No imputation for missing data will be performed for other analysis approaches.

5.4. Meaningful Within-Patient Change Threshold

To aid in the interpretation of the treatment effect on the NSAA total score, the Modified Pediatric Outcomes Data Collection Instrument (PODCI): Transfer and Basic Mobility Core Scale (Pediatric Parent), and the Modified PODCI: Sports and Physical Functioning Core Scale (Pediatric Parent), the meaningful within-patient change thresholds (MWPC) will be estimated for above outcomes using anchor-based methods as described in a supplemental SAP.

To assess whether the treatment effect for each endpoint occurs in the range that patients' consider to be clinically meaningful, eCDFs of within-patient changes from baseline will be provided for:

- Change from Baseline at Week 52 in the NSAA total score
- Change from Baseline at Week 52 in the Modified Pediatric Outcomes Data Collection Instrument (PODCI): Transfer and Basic Mobility Core Scale (Pediatric Parent)
- Change from Baseline at Week 52 in the Modified PODCI: Sports and Physical Functioning Core Scale (Pediatric Parent)

For each endpoint separately, the following figure will be generated, the eCDF curves will display endpoint values (both positive and negative) on the horizontal axis, the cumulative proportion of participants experiencing up to that level of change in the endpoint on the vertical axis (separate curves for dadistrogene movaparvovec and placebo). The graphs will be annotated with a range of *MWPC* values and the proportion of patients in each trial arm whose change-from-baseline exceeds one or more values of *MWPC*.

6. ANALYSES AND SUMMARIES

For analysis purposes, all dated assessments will be categorized into analysis windows. Analysis windows for primary, secondary, and other efficacy endpoints are provided in [Appendix 2.1](#).

6.1. Primary Endpoint

6.1.1. NSAA Total Score

Endpoint: Change from Baseline at Week 52 in the NSAA total score

6.1.1.1. Main Analysis

- Estimand strategy: Primary Estimand ([Section 2.2.1](#)).
- Analysis set: FAS ([Section 4](#)).
- Analysis methodology: Change from baseline will be analyzed using an MMRM approach ([Section 5.2.1.1](#)) including visits through Week 52 where NSAA is assessed (ie, Weeks 9, 18, 35, 52) with additional fixed effects for Baseline NSAA total score (continuous variable), Screening age (continuous variable), Baseline NSAA total score by visit interaction, and Screening age covariate by visit interaction.

To test the primary hypothesis, estimates from the MMRM analysis at Week 52 of the mean changes from Baseline, standard error of each LS mean, and 95% confidence intervals along with the mean treatment group difference, two-sided p-value, and two-sided 95% confidence interval for the mean difference will be provided.

- Intercurrent events and missing data: All available data in the reporting period will be included. The intercurrent events (loss of ambulation or death) and missing data from study discontinuation will be handled in the Primary Estimand as described in [Section 2.2.1](#).
- The number of participants (N), mean, standard deviation (SD), median, first quartile (Q1), third quartile (Q3), minimum, and maximum at Baseline and all visits through Week 52 where NSAA is assessed for observed and changes from baseline NSAA total scores will be provided for fordadistrogene movaparvovec and placebo.
- The fordadistrogene movaparvovec and placebo LS means, standard error of each LS mean, and 95% CIs for the LS means along with the difference between the LS means (fordadistrogene movaparvovec minus placebo) and the corresponding standard error, two-sided p-value, and 95% CI will be provided for change from Baseline in NSAA total score for Week 52 and all visits through Week 52 where NSAA is assessed.

Graphical displays:

- The fordadistrogene movaparvovec and placebo LS means, and 95% CIs for the LS means at each visit will be displayed graphically.

6.1.1.2. Sensitivity Analysis #1

To assess the impact of missing data on the main analysis under the Primary Estimand (Section 6.1.1.1), missing values will be imputed in this analysis.

- Estimand strategy: Primary Estimand (Section 2.2.1).
- Analysis set: FAS (Section 4).
- Analysis methodology: Change from baseline will be analyzed using a copy increments in reference approach (Section 5.3) including covariates for Baseline NSAA total score (continuous variable) and Screening age covariate (continuous variable).
- Intercurrent events and missing data: All available data in the reporting period will be included. The intercurrent events will be handled as described in Section 2.2.1. Missing data will be imputed using the copy increments in reference approach (Section 5.3).
- The fordadistrogene movaparvovec and placebo LS means, standard error of each LS mean, and 95% CIs for the LS means along with the difference between the LS means (fordadistrogene movaparvovec minus placebo) and the corresponding standard error, two-sided p-value, and 95% CI will be provided for change from Baseline in NSAA total score at Week 52.

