2.2.1. Primary Estimand(s)

Primary Estimand: difference in mean change from Baseline at Week 52 in the NSAA total score between fordadistrogene movaparvovec and placebo

- Population: Boys with a genetic diagnosis of DMD who are ambulatory and age ≥ 4 to < 8 years;
- Variable: Change from Baseline at Week 52 in the NSAA total score;
- Intercurrent event(s) and missing data: The potential intercurrent events are death or loss of ambulation. The intercurrent events and missing data will be handled as described below:
 - Death or loss of ambulation: NSAA total score will be set to 0 for all scheduled study visits after death. For participants with LOA, if NSAA test is done post LOA (to confirm a LOA), the NSAA total score from that assessment will be used. A value of 0 will be assumed if NSAA test is NOT DONE post a LOA.
 - Discontinuation from study: missing data from visits after a participant discontinues from the study (with the exception of death) will not be explicitly imputed.
 - Missing data from a participant not able to perform the NSAA due to acute illness or injury considered to be transient, will be assumed to be missing at random and will not be imputed.
- Population-level summary: Difference in mean changes from Baseline at Week 52 in the NSAA total score between fordadistrogene movaparvovec and placebo.

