2.3.1. Sample Size Determination

The sample size of 99 participants in the FAS (see Section 4) is based on the primary efficacy endpoint of change from Baseline at Week 52 in the NSAA total score. The above sample size (assuming 3 participants will drop out of the study prior to Week 52) will provide 98% power to detect a treatment difference (fordadistrogene movaparvovec minus placebo) of 3.0. These calculations are based on $\alpha=0.05$ (two-sided), a 3-look group-sequential design with a gamma family (-1) spending function to determine the efficacy boundary, a gamma family (-4) spending function for the non-binding futility boundary, a common standard deviation of 3.5, and using the normal approximation of the test statistic for the comparison between two means.

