5. GENERAL METHODOLOGY AND CONVENTIONS

The primary analysis will occur after at least 90 FAS participants complete Day 360 (Visit 19) or discontinued from the study prior to Week 52 if they had received Year 1 IP at least

one year prior to the data cutoff. There are 2 options for IAs, both of which are designed to provide data to support an earlier regulatory submission for BLA/MAA as described in [Section 7](#).

As a general rule, all efficacy analyses including the primary endpoint, secondary endpoints, and other endpoints will be conducted based on all FAS participants regardless of adherence to background or protocol mandated glucocorticoid regimens during the first 52 weeks after study drug infusion, unless specified otherwise.

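### Sensitivity analysis #1 would give placebo increments to treated boys who are merely not yet due at Week 52, if the analysis is cut while any are pending

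*SAP*

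**What the plan says.** - **Scope of the imputation.** Section 6.1.1.2 uses the FAS and states "Missing data will be imputed using the copy increments in reference approach". It makes no distinction by cause.
- **The rule.** Under Section 5.3, "missing data in the fordadistrogene movaparvovec group will be imputed under a missing not at random (MNAR) assumption": a treated boy keeps his last observed value and then follows the placebo group's changes. Missing placebo values are imputed under MAR. The rationale given is that boys who drop out resume disease progression, as a worst case.
- **The population.** Section 4 defines the FAS as boys randomized and dosed on Day 1, leaving out siblings and those meeting exclusion criterion 15. It sets no minimum follow-up.
- **The timing.** Section 5: "The primary analysis will occur after at least 90 FAS participants complete Day 360 (Visit 19) or discontinued from the study". A footnote in Section 4 repeats this. Section 2 instead places the primary analysis at the point when every participant has completed Week 52 or withdrawn.
- **The estimand.** Section 2.2.1 says that NSAA data missing "due to acute illness or injury considered to be transient, will be assumed to be missing at random and will not be imputed".
- **The tipping point.** Section 6.1.1.3 announces a tipping-point analysis in one sentence and does not say which missing values are shifted.

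**The concern.** A boy whose Week 52 visit has not fallen due at the data cut-off has not left the study, and his missing value says nothing about his response. The reason Section 5.3 gives for placebo increments does not apply to him. The text still sweeps him in, because the FAS has no follow-up condition and the imputation rule has no cause condition. The arms are also treated differently: the same administrative gap is penalised on active treatment and left neutral on placebo.

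At stake is what sensitivity analysis #1 measures. It is meant to show whether the primary result survives an unfavourable assumption about missing data. If some imputed values are only pending, part of any drop in the estimate would come from the calendar and not from dropout.

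**Working it through.** **1. The plan's own figure (Section 2.3.1).** "The sample size of 99 participants in the FAS", 3 of them dropping out, "a common standard deviation of 3.5", and the claim that this "will provide 98% power to detect a treatment difference (fordadistrogene movaparvovec minus placebo) of 3.0". With 96 evaluable at 2:1 (64 and 32):

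- SE = 3.5 × √(1/64 + 1/32) = 3.5 × 0.2165 = 0.758
- Fixed-design power = Φ(3.0/0.758 − 1.96) = Φ(2.00) = 97.7%; with all 99 it is 98.0%
- Three looks at 30/99, 60/99 and 1 with gamma(−1) efficacy spending, by simulation: 97.0% (96 boys) and 97.4% (99 boys); with the futility boundary followed, 96.8% and 97.3%

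The stated 98% is reproduced to within about one percentage point. The design figure itself is sound.

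**2. How many boys could be pending.** At most 99 − 90 = 9. The trigger is a minimum, so the number can also be 0. At 2:1, 9 pending boys are 6 active and 3 placebo. This split is an assumption.

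**3. Effect of the rule.** A pending treated boy keeps the benefit reached at his last visit and adds the placebo change thereafter. His expected advantage over placebo at Week 52 is therefore the benefit already reached, whatever the placebo course. So:

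Dilution = (pending active / 66) × (3.0 − benefit at last visit)

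The SAP gives no time course. Assume that the 3.0 points build linearly over the target days in Appendix 2.1 (60, 120, 240, 360). With 6 active boys pending:

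| Last NSAA | Calculation | Dilution | Expected difference | Fixed-design power |
|---|---|---|---|---|
| Week 35 | (6/66) × 3 × (1 − 240/360) | 0.09 | 2.91 | 97.0% |
| Week 18 | (6/66) × 3 × (1 − 120/360) | 0.18 | 2.82 | 96.1% |
| Week 9 | (6/66) × 3 × (1 − 60/360) | 0.23 | 2.77 | 95.5% |
| No post-baseline value | (6/66) × 3 | 0.27 | 2.73 | 94.9% |
| Any visit, benefit plateaued | (6/66) × 0 | 0 | 3.00 | 97.7% |

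**4. Range over the number pending.**

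- None pending: 0.
- Six pending (4 active): 3.0 falls to between 2.94 and 2.82.
- All nine in the active arm (extreme): between 2.86 and 2.59.
- For comparison, the 3 planned dropouts alone (2 active at 2:1): between 2.97 and 2.91.

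**5. Against the noise.** 0.09/0.758 = 0.12 standard errors; 0.18/0.758 = 0.24 standard errors.

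**The case against.** The strongest reply is that the SAP never says pending boys are imputed. Section 2 would leave none pending, and the version history says the Section 4 footnote was added to clarify the FAS for this analysis, so its one-year clause may have been meant to restrict the FAS. Part of this stands: the problem arises only if the analysis is cut under the Section 5 trigger with boys outstanding. However, the footnote as worded states when the analysis occurs, not who belongs to the FAS, and the Section 2 sentence conflicts with it. The plan does not settle the question.

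A second reply is that stressing every missing value is conservative, and that a sensitivity analysis departs from MAR on purpose. That is fair for dropout. It is weaker for values missing only through the cut-off, because Section 5.3 offers no reason to think they are informative.

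For transient illness the point is narrow. Appendix 1 gives the model as ANCOVA, so a missed earlier visit does not matter if Week 52 was observed. Only a Week 52 assessment missed throughout the Day 300 to 390 window is touched.

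A reader might infer more than the document supports:

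- **That dilution is built in.** It is not: copy increments preserve the benefit already reached.
- **That most imputed active values would be administrative.** With 6 active pending and 2 active dropouts it is 6/8 = 75%, but both counts are assumed. With 2 or fewer active boys pending (about 3 pending in all) it is no longer a majority.
- **That the result would look falsely fragile.** A shift of 0.12 to 0.24 standard errors does not show that at the design effect.
- **That the tipping-point analysis penalises the same values.** Section 6.1.1.3 does not say which values it shifts.

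**Conclusion.** The concern holds conditionally. If the analysis is cut after at least 90 boys while others are pending, the literal rule treats pending treated boys as dropouts and pending placebo boys as missing at random. Where benefit is still accruing, this biases sensitivity analysis #1 towards a smaller effect. The central illustration is 0.09 to 0.18 points out of 3.0. It rests on three assumptions that are not in the SAP: 9 boys pending, a 2:1 split among them, and linear accrual.

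The confirmatory MMRM is not affected, because it leaves such visits missing under MAR. The size is modest. The case for changing the text is that the bias is one-sided, lies outside the plan's own rationale, and is easily removed.

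**What to change.** 1. Reconcile the statement in Section 2 with Sections 4 and 5 on when the primary analysis occurs, and state whether boys dosed less than one year before the cut-off belong to the FAS for it.
2. In Sections 5.3 and 6.1.1.2, apply copy increments in reference only to values missing after study discontinuation. Impute Week 52 values missing because of the data cut-off, or because of transient illness or injury as in Section 2.2.1, under MAR within arm.
3. In Section 6.1.1.3, state the same scope for the tipping-point shifts.

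The cost is a few sentences and one flag for the reason a value is missing in the imputation dataset, settled before unblinding. No new data are needed, and neither the primary analysis nor the error control changes. Free improvement.

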6.1.1.3. Sensitivity Analysis #2

A tipping point analysis will be performed to assess the impact of missing data on the main analysis under Primary Estimand (Section 6.1.1.1).

6.1.1.4. Sensitivity Analysis #3

There was a quality event investigation (PR2222549) involving Clinical Site 1024 based on quality issues in the assessment of NSAA. Specifically, there were significant quality concerns around NSAA assessments done by one of the raters at this site. To evaluate the impact of these findings on the primary analysis, a sensitivity analysis will be done by excluding all NSAA assessments conducted by this rater.

6.1.1.5. Sensitivity Analysis #4

The difference between screening age and age at dosing due to pause(s) in dosing during the conduct of the study could impact the evaluation of age effect in the model. To assess this impact, a sensitivity analysis of the primary analysis would be conducted by replacing age at screening with age at dosing as the age-based covariate.

6.1.1.6. Supplementary Analysis

This analysis is the same as the main analysis in Section 6.1.1.1 except data from sibling(s) will be added to the data from the FAS if applicable. No graphics will be produced for this analysis.

- Estimand strategy: Primary Estimand (Section 2.2.1).

- Analysis set: FAS ([Section 4](#)) plus data from sibling(s) ([Section 2.3.3](#)).
- Analysis methodology: Change from baseline will be analyzed using an MMRM approach ([Section 5.2.1.1](#)) including visits through Week 52 where NSAA is assessed (ie, Weeks 9, 18, 35, 52) with additional fixed effects for Baseline NSAA total score (continuous variable), Screening age covariate (continuous variable), Baseline NSAA total score by visit interaction, and Screening age covariate by visit interaction.
- Intercurrent events and missing data: All available data in the reporting period will be included. The intercurrent events and missing data will be handled as described in [Section 2.2.1](#).
- N, mean, SD, median, Q1, Q3, minimum, and maximum at Baseline and all visits through Week 52 where NSAA is assessed for observed NSAA total scores and changes from baseline will be provided for fordadistrogene movaparvovec and placebo.
- The fordadistrogene movaparvovec and placebo LS means, standard error of each LS mean, and 95% CIs for the LS means along with the difference between the LS means (fordadistrogene movaparvovec minus placebo) and the corresponding standard error, two-sided p-value, and 95% CI will be provided for change from Baseline in NSAA total score for all visits through Week 52 where NSAA is assessed.

6.1.1.7. Meaningful Within-Patient Change Threshold

eCDF curves of change from Baseline in the NSAA total score at Week 52 will be provided as described in [Section 5.4](#).

6.2. Secondary Endpoints

6.2.1. Biceps Muscle Biopsies

Endpoints:

- Change from Baseline in percent normal mini-dystrophin expression level in biceps brachii muscle biopsies at Day 360 (Week 52) using an LC-MS assay (primary peptide is LLQV).
- Change from Baseline in percent normal mini-dystrophin expression level in biceps brachii muscle biopsies at Day 360 (Week 52) using an LC-MS assay (supplementary peptide is LEMP).
- Change from Baseline in percent of muscle fibers expressing mini-dystrophin in biceps brachii muscle biopsies at Day 360 (Week 52) as assessed by immunofluorescence.

6.2.1.1. Main Analysis

- Estimand strategy: Secondary Estimand ([Section 2.2.2](#)).

- Analysis set: FAS ([Section 4](#)).
- Analysis methodology: Change from baseline will be analyzed using an ANCOVA model ([Section 5.2.1.3](#)) including terms for treatment group, and Screening age covariate (continuous variable).
- Intercurrent events and missing data: All available data in the reporting period will be included. The intercurrent events and missing data will be handled as described in [Section 2.2.2](#)
- N, mean, SD, median, Q1, Q3, minimum, and maximum at Baseline (only for LC-MS assay) and Day 360 (Week 52) for the observed value and change from baseline will be provided for fordadistrogene movaparvovec and placebo.
- The fordadistrogene movaparvovec and placebo LS means, standard error for each LS mean, and 95% CIs for the LS means along with the difference between the LS means (fordadistrogene movaparvovec minus placebo) and the corresponding standard error, two-sided p-value, and 95% CI at Day 360 (Week 52) will be provided.

Graphical displays:

- The distribution of changes from baseline at Day 360 (Week 52) for fordadistrogene movaparvovec and placebo will be displayed graphically using box plots.

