1. VERSION HISTORY

Table 1. Summary of Changes			
Version/ Date	Associated Protocol Amendment	Rationale	Specific Changes
9 08 Apr 2024	Amendment 15 28-Dec-2023	To clarify the timing of primary analysis based on protocol	Section 5 Added text “The primary analysis will occur after at least 90 FAS participants complete Day 360 (Visit 19) or discontinued from the study prior to Week 52 if they had received Year 1 IP at least one year prior to the data cutoff.”
		Due to the transfer of the viral vector shedding assay to an internal lab during the course of the study and some differences in the results between the 2 assays, the analysis for endpoint viral vector levels are removed from the planned analysis as they may include data from both assays. switch of labs for the	Sections 6.3.8, Appendix 1 Removed analysis for viral vector levels endpoint
		To clarify the FAS definition for PCD analysis and align with protocol	Section 4 Changed the name of Full Analysis Set (FAS) to Full Analysis Set (FAS) (through Week 52) Added footnote to clarify the FAS for PCD analysis
		To evaluate the treatment effect more comprehensively using multiple endpoint	Sections 5.2.4, 6.4 Added global statistical test analysis for specified multiple functional endpoints
		To better present the analysis results	Sections 6.1.1, 6.2.2, 6.2.3, 6.2.4, 6.2.5, Appendix 1 Removed model-based summary of LS means at Week 52 for each age. Added standard error of each LS mean and estimated difference in LS mean in the summary Removed graph for Mean (SD) change from Baseline at Week 52 by age at the Screening visit.

		To update the ANCOVA analysis for biceps muscle biopsies by removing Baseline factor as the values at Baseline are expected to be around 0 and exhibit extremely low variability	Sections 6.2.1.1, 6.2.12, Appendix 1 Removed text “Baseline (continuous variable)” from the ANCOVA model
		To evaluate actigraphy endpoints based on statistical model and aid in the interpretation of the treatment effect	Section 5.4, 6.3.2, Appendix 1 Added clarification that mean will be calculated for visits with at least 4 compliant days Added MMRM analysis for all actigraphy endpoints Added 95 th percentile of cadence actigraphy endpoint for Screening age strata subgroup analysis
		To correct typographical errors in the subgroup analysis for number of skills endpoints	Section 6.4.1 Removed MMRM description for NSAA total score Added the description of Binomial with logit link function

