3.2. Secondary Endpoint(s)

1. Change from Baseline in percent normal mini-dystrophin transgene protein expression level in biceps brachii muscle biopsies at Day 360 (Week 52) using an LC-MS assay

The LC-MS assay measures the LLQVAVEDR (LLQV) peptide that detects full-length endogenous dystrophin as well as the mini-dystrophin transgene protein. The expression level will be provided from the vendor and is expressed as %normal, with normal defined by full length dystrophin from non-dystrophic control samples. Levels below the LLOQ will be imputed as 0.5*LLOQ. The LC-MS assay also measures the LEMPSSLMLEVPTHR (LEMP) peptide which quantifies only the mini-dystrophin transgene levels. The baseline LEMP peptide level in the biceps brachii muscle biopsy is expected to be below the LLOQ due to the absence of the mini-dystrophin transgene prior to treatment.

2. Change from Baseline in percent of muscle fibers expressing mini-dystrophin transgene protein in biceps brachii muscle biopsies at Day 360 (Week 52) as assessed by immunofluorescence.

Muscle fibers expressing mini-dystrophin transgene protein will be evaluated by immunofluorescent staining using the mini-dystrophin specific antibody that only recognizes the mini-dystrophin transgene protein.

For the participant in Study C3391003 , a global threshold for calculating the percentage of mini-dystrophin positive fibers was applied based on all baseline samples from the 19 ambulatory participants

3. Change from baseline at Week 52 in serum CK concentration.

The CK results reported by the central laboratory and each local laboratory will be converted to conventional units of measurement, if necessary. These unit-standardized results will be used for analysis purposes.

4. Number of skills gained at Week 52 based on the individual items of the NSAA.

The number of skills gained at Week 52 is the total number of skills with a response of 0 at Baseline and a response of either 1 or 2 at Week 52.

5. Number of skills either improved or maintained at Week 52 based on the individual items of the NSAA.

The number of skills either improved or maintained at Week 52 is the total number of skills with:

- A response of 0 at Baseline and a response of either 1 or 2 at Week 52, or
- A response of 1 at Baseline and a response of 1 or 2 at Week 52, or
- A response of 2 at Baseline and a response of 2 at Week 52.

6. Change from Baseline at Week 52 in the 10 meter run/walk velocity.

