5.2.1.3. Analysis of Covariance (ANCOVA)

The analysis of covariance (ANCOVA) model assumes that the error term has a normal distribution. The dependent variable will be the specific endpoint and the model will include a term for treatment group (as a categorical variable). Additional terms (eg, covariates and interaction effects) to be included in the model are specified in [Section 6](#).

The model-adjusted estimates for the endpoint for each treatment group will be provided using the LS means, standard error of each LS mean, and their 95% CIs calculated based on the average continuous covariate values. The differences in LS means (fordadistrogene movaparovec minus placebo) will be provided along with the corresponding standard error, two-sided p-value (unadjusted for multiplicity) and 95% CI (unadjusted for multiplicity).

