Change from Baseline at Week 52 in the NSAA total score	Geographic region subset	FAS	All available data will be included Missing data will not be explicitly imputed	MMRM with treatment group, visit, and treatment group by visit interaction with additional fixed effects for baseline, baseline by visit interaction, screening age covariate, and screening age by visit interaction
Muscle Biopsies				
Change from Baseline in percent normal mini-dystrophin expression level at Day 360 (Week 52)	Summary Box plots	FAS	All available data will be included Missing data will not be imputed	N/A
Change from Baseline in percent normal mini-dystrophin expression level at Day 360 (Week 52)	Main analysis	FAS	All available data will be included Missing data will not be imputed	ANCOVA with additional terms for Baseline and Screening age covariate

090177e1a0727983\Approved\Approved On: 16-Apr-2024 16:39 (GMT)

Endpoint	Analysis Type	Population	Data Inclusion and Rules for Handling Intercurrent Events and Missing Data	Analysis Model
Change from Baseline in percent normal mini-dystrophin expression level at Day 360 (Week 52)	Supplementary	FAS plus siblings	All available data will be included Missing data will not be imputed	ANCOVA with additional terms for Baseline and Screening age covariate
Change from Baseline in percent of muscle fibers expressing mini-dystrophin at Day 360 (Week 52)	Summary Box plots	FAS	All available data will be included Missing data will not be imputed	N/A
Change from Baseline in percent of muscle fibers expressing mini-dystrophin at Day 360 (Week 52)	Main analysis	FAS	All available data will be included Missing data will not be imputed	ANCOVA with additional terms for Baseline and Screening age covariate
Change from Baseline in percent of muscle fibers expressing mini-dystrophin at Day 360 (Week 52)	Supplementary	FAS plus siblings	All available data will be included Missing data will not be imputed	ANCOVA with additional terms for Baseline and Screening age covariate
CK				
Change from Baseline at Week 52 in serum CK concentration	Summary (observed, change from baseline, and percentage change from baseline) Box plots (percent change from Baseline)	FAS	All available data will be included Missing data will not be imputed	N/A

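### The biopsy ANCOVA pools one residual variance over two arms whose spread should differ greatly, so the treated-arm interval is too narrow and the placebo and difference intervals are too wide

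*SAP*

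**What the plan says.** Section 6.2.1.1 of the SAP covers three biopsy endpoints: LC-MS with LLQV (the primary peptide), LC-MS with LEMP (supplementary), and the percentage of positive fibres by immunofluorescence. For all three, "Change from baseline will be analyzed using an ANCOVA model", with terms for treatment and screening age. The planned output includes "standard error for each LS mean, and 95% CIs for the LS means along with the difference between the LS means". Section 6.2.1.2 uses the same model with siblings added.

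Section 5.2.1.3 describes a single error term: "The analysis of covariance (ANCOVA) model assumes that the error term has a normal distribution". Nothing there or in Section 6.2.1 provides for variances that differ by arm.

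Three other statements bear on the spread expected without transgene:

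- Section 3.2 says that the LEMP level at baseline "is expected to be below the LLOQ due to the absence of the mini-dystrophin transgene prior to treatment", and that "Levels below the LLOQ will be imputed as 0.5*LLOQ".
- Section 3.2 also says that the immunofluorescence antibody recognises only the transgene protein, whereas LLQV detects endogenous dystrophin as well.
- Section 1 explains that Baseline was dropped from the biopsy ANCOVA because "the values at Baseline are expected to be around 0 and exhibit extremely low variability".

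The main and supplementary biopsy rows of Appendix 1 still specify "ANCOVA with additional terms for Baseline and Screening age covariate".

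**The concern.** Under Section 2.3, placebo boys receive no vector before Day 390, and under Section 2.3.2 the reporting period ends before the Year 2 infusion. Their Week 52 muscle should therefore resemble untreated muscle, which the SAP itself expects to show almost no spread. Treated boys will differ from one another in expression. A pooled residual variance averages the two arms and describes neither.

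The stated objective is to quantify expression in treated boys. The model-based interval for the treated-arm mean is the only interval planned for that quantity, and pooling makes it too short. Pooling also puts a wide interval around placebo values that barely differ and, under 2:1 allocation, widens the interval for the difference. The subset is small (about 15 biopsied participants, at most 33), so the effect can be seen in the reported numbers.

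**Working it through.** The SAP states no precision figure for the biopsy endpoints. Its only power figure is for the NSAA and does not bear on this point.

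**Inputs**

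- Allocation is 2:1 (Section 2.3).
- The biopsy subset is about 15 to 33 (Section 2.3.3). This is taken as na:np = 10:5 or 22:11, assuming that the subset keeps the 2:1 split.
- r = placebo SD / active SD of the change. It is not given, and is varied from 0 to 1.
- All widths are in units of the active-arm SD, so no SD value is needed.

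**Standard errors (two groups, age omitted)**

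Pooled variance: sp² = [(na − 1) + (np − 1)r²] / (na + np − 2).

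At r = 0:

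- Treated-arm SE, pooled over own: √(9/13) = 0.83 at 10:5 and √(21/31) = 0.82 at 22:11.
- Difference SE, pooled over unequal-variance: √[(9/13)(15/5)] = 1.44 at 10:5 and √[(21/31)(33/11)] = 1.43 at 22:11.

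At r = 0.5 and 10:5, sp² = (9 + 4 × 0.25)/13 = 0.769. The treated-arm ratio is then 0.88, and the difference ratio is √[0.769 × 0.3 / (0.1 + 0.25/5)] = 1.24.

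The excess width of the difference interval comes from the unequal allocation. At 1:1 the two SEs of the difference are equal.

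**95% half-widths (common variance / arm-specific variance)**

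| na:np | r | Treated mean | Difference | Placebo mean |
|---|---|---|---|---|
| 10:5 | 0 | 0.568 / 0.715 | 0.985 / 0.715 | 0.804 / 0 |
| 10:5 | 0.5 | 0.599 / 0.715 | 1.038 / 0.837 | 0.847 / 0.621 |
| 22:11 | 0 | 0.358 / 0.443 | 0.620 / 0.443 | 0.506 / 0 |
| 22:11 | 0.5 | 0.379 / 0.443 | 0.656 / 0.533 | 0.535 / 0.336 |

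As intervals, including the change in degrees of freedom, the difference at r = 0 is 38% to 40% wider than the unequal-variance one (0.985/0.715 and 0.620/0.443).

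**Coverage of the SAP's model with age included**

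Simulation of the ANCOVA with treatment and age: normal errors, age uniform on 4 to 8, 8,000 runs per setting, Monte Carlo error about 0.3 percentage points.

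| na:np | r | Treated mean | Placebo mean | Difference |
|---|---|---|---|---|
| 10:5 | 0 | 89.7% | 100% | 98.7% |
| 10:5 | 0.5 | 91.9% | 99.5% | 97.9% |
| 10:5 | 1 | 94.9% | 94.8% | 94.8% |
| 22:11 | 0 | 89.7% | 100% | 99.2% |
| 22:11 | 0.5 | 91.6% | 99.8% | 98.2% |
| 22:11 | 1 | 94.9% | 94.9% | 94.7% |

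A separate run of 20,000 replicates at r = 0 gave 89.6% and 89.2% for the treated mean, and 98.7% and 99.1% for the difference.

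**The obvious remedy**

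Suppose the residual variance is made group-specific but the single age slope is kept. Each arm then contributes information on the slope roughly in proportion to (n − 1)/variance, if age spread is similar in both arms. At r = 0.25 the placebo share is (4 × 16)/(4 × 16 + 9) = 64/73 = 88% at 10:5 and (10 × 16)/(10 × 16 + 21) = 160/181 = 88% at 22:11. At r = 0 the placebo variance cannot be estimated at all.

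**The case against.** **Placebo variance of exactly zero.** A reader might infer that every placebo change is 0 on all three endpoints. The documents do not support that. The argument is literal only for LEMP, and only if both samples are below the LLOQ; LEMP is the supplementary peptide. LLQV also measures endogenous dystrophin, so its placebo changes can carry biopsy and assay noise. Fibre positivity is set by a global threshold derived from baseline samples, so small non-zero changes are possible there too. The statements about low variability concern Baseline, and carrying them to placebo at Week 52 is a strong inference but still an inference. All of this stands, and it is why r is shown as a range.

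**Little depends on it.** The biopsy endpoints are not in the fixed testing sequence of Section 5.1, and the error on the contrast is conservative. A reader might infer that an efficacy claim is inflated, but the documents give no basis for that.

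**The information is recoverable.** Section 6.2.1.1 also requires N, mean and SD by arm, plus box plots, so a reader could compute the treated-arm interval. This mitigates the problem, but the published model-based interval would still be wrong.

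**The common slope.** A group-specific variance option alone would let the placebo boys dominate the age adjustment. This objection stands and changes the remedy.

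**Conclusion.** The common-variance ANCOVA misstates precision on the biopsy endpoints whenever placebo changes vary less than treated changes, as the SAP's own description leads one to expect. At 2:1 with 15 to 33 biopsies, the nominal 95% interval for the treated-arm mean covers about 89-90% at r = 0 and 91-92% at r = 0.5. The difference interval over-covers at about 99% and 98%, and the placebo interval is far too wide. At r = 1 there is no error.

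The figures rest on the assumed r, on normal errors and on the subset keeping the 2:1 split. The effect should be largest for LEMP, probably close to that for immunofluorescence, and smaller for LLQV. The change is worth making because quantifying expression in treated boys is the stated objective, but no confirmatory conclusion depends on it.

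The Baseline term in Appendix 1 is a separate contradiction between two parts of the current SAP. It neither adds to nor explains the variance problem. For LEMP at the assay floor, Baseline would be a constant and could not be separated from the intercept.

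**What to change.** In Sections 6.2.1.1 and 6.2.1.2:

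1. Report the treated-arm mean change with an interval from that arm's own variance, either a t-interval or one age-adjusted within the arm.
2. Report the contrast with an unequal-variance standard error, either Welch or heteroscedasticity-consistent.
3. Do not combine a group-specific residual variance with one common age slope, for the reasons shown above.

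Separately, delete Baseline from the main and supplementary biopsy rows of Appendix 1, for both mini-dystrophin expression and fibre percentage, so that they agree with Sections 6.2.1.1 and 6.2.1.2.

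The cost is SAP wording and a small amount of code, with no new data and no change to conduct. There are two modest downsides. A Welch contrast is not age-adjusted. The treated-arm interval also becomes wider: at r = 0, by about 26% at 10:5 (0.715/0.568) and 24% at 22:11 (0.443/0.358).
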